4.3.1 Disposition of patients

4.3.1.1 Participant disposition

A detailed description of participant accountability including count of participants by analysis populations, screen failure participants with reasons for screen failure, participants who did not complete the study observation period along with the main reason for study discontinuation (including the relationship to COVID19 for the reasons “Other” if any), and participants who requested permanent treatment discontinuation with the main reason for permanent treatment discontinuation (including the relationship to COVID19 for reasons “Adverse event”, “Withdrawal by subject” and “Other” if any), will be generated by cohorts.

Participant disposition by centre/site will also be performed.

All withdrawals from the study, taking place on or after study intervention intake, will be listed (including the column “Related to COVID19” if applicable).

A listing of patients with treatment discontinuation will be provided (including the column “Related to COVID19” if applicable).

4.3.1.2 Protocol deviations

Individual deviations to inclusion and exclusion criteria as reported by the Investigator will be listed. Major and critical deviations, other than those involving inclusion/exclusion, will be listed by participant (including the column “Related to COVID19” if applicable).

4.3.1.3 Analysis populations

The number of participants included in each study population (safety population and efficacy populations (ITT and mITT) will be provided. Participants (and visits for mITT population) with reasons of exclusion will be listed.

4.3.2 Analyses of baseline characteristics

4.3.2.1 Participant demographic characteristics, medical history, and diagnoses

Continuous variables (age, weight and body mass index [BMI]) and qualitative variables (gender, race, ethnicity, and BMI [<20 / ≥ 20]) will be summarized by cohorts, by descriptive statistics (summary tables) for the mITT population and for additional population if relevant (eg, if many participants from the mITT population are not part of the safety population).

Medical/surgical histories will be coded using the version of medical dictionary for regulatory activities (MedDRA) in effect at Sanofi at the time of each database lock.

Medical/surgical histories will be summarized by cohort and by system organ class (SOC), high level term (HLT) and preferred term (PT) and listed.

Disease characteristics (ie, years since AD diagnosis at baseline) will be summarized by descriptive statistics for the mITT population.

Matched participants will be listed.

4.3.2.2 Baseline efficacy parameters

For efficacy parameters, baseline is defined as the last available and evaluable value at Day 1 (Week 0) (or at Screening if the value at Day 1 is not available) for patients and healthy volunteers.

For TEWL data, the baseline value will be defined for each skin group and each number of STS (before/without STS, after 5 STS, after 10 STS, after 15 STS and after 20 STS). In addition for before/without STS, a baseline will be defined for each spot, due to strong variability between the 3 adjacent spots in a similar study conduct by the Sponsor.

Baseline efficacy values will be presented along with the subsequent efficacy values assessed during the on-treatment period.

4.3.2.3 Baseline safety parameters

For vital sign parameters, baseline will be defined as the last available and evaluable value before and closest to the first dose of IMP for patients and as the last available and evaluable value at Day 1 (Week 0) for healthy volunteers.

Baseline safety values will be presented along with subsequent safety values assessed during the study.

4.3.2.4 Extent of study treatment exposure and compliance

The extent of study treatment exposure and compliance will be assessed and summarized for patients' cohort within the safety population.

A listing of patients receiving IMP from specified batch (patient, IMP, and IMP batch number) will be performed by patient.

Extent of IMP exposure

Duration of IMP exposure is defined regardless of unplanned intermittent discontinuations as:

- Dose regimen 1: the last dose date - first dose date +28 days.
- Dose regimen 2: the last dose date - first dose date +14 days.

If the patient's date of last dose is unknown, his/her last IMP dispensing date will be used in its place.

Duration of exposure will be summarized in patients' cohort using descriptive statistics as quantitative and qualitative variables (1 day / 2 to 15 days / 16 to 29 days / 30 to 43 days / 44 to 57 days / 58 to 71 days / 72 to 85 days / 86 to 99 days / 100 to 113 days / 114 to 155 days / 156 to 197 days). This description could be performed by trial impact (disruption) due to COVID19 (without and with).

Compliance

A given administration will be considered noncompliant if the patient did not take the planned dose of treatment as required by the protocol. No imputation will be made for patients with missing or incomplete data.

Percentage of compliance for a patient will be defined as the number of administrations the patient was compliant divided by the total number of administrations the patient was planned to take (the number of doses missed due to interruptions at Investigators' judgment will not be subtracted) on or before the last IMP administration date.

Treatment compliance, above-planned and under-planned dosing percentages will be summarized descriptively. The percentage of patients with compliance <80% will be summarized. In addition, number and percentage of patients with at least 1 above-planned dosing administration will be

given, as well as the number and percentage of patients with 0,]0, 20%], and >20% under planned dosing administrations.

4.3.2.5 *Prior/Concomitant medication/therapy*

All medications taken during the study will be coded using the version of world health organization drug dictionary (WHO-DD) in effect at Sanofi at the time of each database lock.

Medications will be classified into three categories, prior, concomitant and post-treatment medications, according to the following rules:

- Prior medications are those the participant used before the first IMP administration. Prior medications can be discontinued before the first IMP administration or can be ongoing during the treatment phase.
- Concomitant medications are any medications received by the participant concomitantly to the IMP, from the first IMP administration to the last IMP administration + 28 and 14 days for regimen dose 1 and regimen dose 2 respectively.
- Post-treatment medications are those the participant took in the period running from the end of the concomitant medications period up to the end of the study.

A given medication can be classified simultaneously as a prior, concomitant and post-treatment medication. If a medication date or time is missing or partially missing and it cannot be determined whether it was taken prior or concomitantly or post, it will be considered as prior, concomitant, and post-treatment medication.

For each category of medications, medications will be summarized by cohort according to the WHO-DD dictionary, considering the first digit of the anatomic therapeutic class (ATC) (anatomic category) and the first three digits of the ATC class (therapeutic category). All ATC codes corresponding to a medication will be summarized, and participants will be counted once in each ATC category (anatomic or therapeutic) linked to the medication. Therefore, participants may be counted several times for the same medication. Concomitant medications will be listed separately by participants.

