1.1 STUDY DESIGN

Study design

This is a Phase 4 open-label, exploratory study in three sites evaluating the effect of dupilumab on skin barrier function (as measured by transepidermal water loss (TEWL) before and after skin tape stripping [STS]) in pediatric patients aged between ≥ 6 and <12 years old with moderate-to-severe atopic dermatitis (AD) with a healthy volunteer cohort as a reference comparator. Patients with moderate-to-severe AD will be included in the US site and patients with severe AD will be included in the EU site (UK). One more US site was initiated because the recruitment at the first US site was insufficient.

Sample size

Approximately 24 pediatric patients with moderate-to-severe AD will be enrolled. An approximately equal number of age, gender, location of targeted lesion area and site matched healthy volunteers serving as a reference comparator cohort will also be enrolled.

Randomization

Not applicable.

Treatment received

Study participants will be assigned to study intervention as described below:

- Up to 24 pediatric patients with moderate-to-severe AD will receive dupilumab.
- Dose regimen 1: children with baseline $15 \text{ kg} \leq \text{body weight} < 30 \text{ kg}$ will receive a subcutaneous (SC) loading dose of dupilumab 600 mg (2 injections of dupilumab 300 mg) on Day 1 (Week 0), followed by every 4-week SC dosing of dupilumab 300 mg from Week 4 to Week 12.
- Dose regimen 2: children with baseline $30 \text{ kg} \leq \text{body weight} < 60 \text{ kg}$ will receive a SC loading dose of dupilumab 400 mg (2 injections of dupilumab 200 mg) on Day 1 (Week 0), followed by bi-weekly SC dosing of dupilumab 200 mg from Week 2 to Week 14.

The treatment will be given to the pediatric patient (≥ 6 and < 12 years of age) depending on its body weight.

Duration of study period

This is a 32-week study with a 4-week screening period, 16-week treatment phase designed to investigate dupilumab's effect on skin barrier function in approximately 20 pediatric patients with moderate-to-severe AD, and a 12-week follow-up period.

The graphical study design is detailed in [Section 8 \(Appendix A\)](#).

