- c Dose regimen 1: Children with baseline $15 \text{ kg} \leq \text{body weight} < 30 \text{ kg}$ will receive a SC loading dose of dupilumab 600 mg (2 injections of dupilumab 300 mg) on Day 1 (V02), followed by every 4-week SC dosing of dupilumab 300 mg until Week 12 (at Week 0 [(Day 1], Weeks 4, 8, and 12).
- Dose regimen 2: Children with baseline $30 \text{ kg} \leq \text{body weight} < 60 \text{ kg}$ will receive a SC loading dose of dupilumab 400 mg (2 injections of dupilumab 200 mg) on Day 1 (V02), followed by bi-weekly SC dosing of dupilumab 200 mg until Week 14 (at Week 0 (Day 1), Weeks 2, 4, 6, 8, 10, 12, and 14).
- d Assessments on treatment days have to be conducted before administration of dupilumab.
- e Predefined lesional and non-lesional skin areas. TEWL will be measured at each of the 3 closely adjacent spots within the predefined skin areas at all visits without STS and before STS at visits with STS.
- f TEWL will be conducted before STS and then after 5, 10, 15, and 20 STS in lesional skin and non-lesional skin.
- g At Weeks 0, 8, 16, and 28, STS will be conducted on the first spot within the predefined skin area. At Week 2 STS will be conducted on the second spot within the predefined skin area. At Weeks 4, 12, and 22 STS will be conducted on the third spot within the predefined skin area. TEWL will be assessed in lesional skin and non-lesional skin before STS and after 5, 10, 15, and 20 STS. All skin tape strips should be collected and stored.
- h In case STS assessment is to be conducted at an unscheduled visit or at a premature EoT visit the assessment should be conducted at that spot of the skin area, for which the period passed since the last STS assessment is the longest.
- i OCT will be done before STS/TWL, and FTIR will be done before and during STS.
- j Worst itch NRS, Sleep disturbance NRS and Skin pain NRS will be assessed daily from Day -7 to Day -1; daily from Day 1 to Week 4 and then 7 days prior to Week 6, Week 8, Week 12, Week 16, Week 22, and to Week 28 by e-diary.
- k eDiary will be dispensed to the patients at screening (Visit 01) and will be collected on Week 28 (Visit 14). The PROs will be administered to patients via eDiary. Patients will bring the eDiary to the site at each visit, and it will be reviewed for any questionnaires omission and dispensed back to patients at each visit.

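### The compliance percentage leaves out planned doses missed at the end of the course, so a child who misses the last dose or doses before Week 16 can be reported as 100% compliant

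*SAP*

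**What the plan says.** Section 4.3.2.4 first defines a miss: "A given administration will be considered noncompliant if the patient did not take the planned dose of treatment as required by the protocol". A patient's compliance is then the "number of administrations the patient was compliant divided by the total number of administrations the patient was planned to take". A parenthesis adds that "the number of doses missed due to interruptions at Investigators' judgment will not be subtracted", and the sentence closes with "will not be subtracted) on or before the last IMP administration date", which limits the planned administrations to those due no later than the date of the last one given. One headline summary rests on this figure: "The percentage of patients with compliance <80% will be summarized".

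The planned courses are in section 1.1 and in footnote c of the Appendix B schedule. Regimen 1 has a Day 1 loading dose, "followed by every 4-week SC dosing of dupilumab 300 mg from Week 4 to Week 12"; the footnote lists Week 0 and "Weeks 4, 8, and 12", which is 4 administrations. Regimen 2 has Day 1 and then every second week to Week 14, which the footnote lists as 8 administrations. The primary endpoint (section 4.1.2) is read at Week 16.

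**The concern.** A skipped planned dose meets the SAP's definition of noncompliance, yet whether it counts depends on what happens next. If a later dose is given, the miss enters the denominator and lowers the percentage. If none is given, the miss drops out. The clause that keeps interrupted doses in the denominator does not help here, because it too works only up to the cut-off date.

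The omissions that drop out are therefore those closest to the Week 16 measurement. The case that matters is a child who skips the last dose or doses without formally discontinuing and still attends Week 16. That child contributes to the endpoint and appears as fully compliant. A reader who uses the compliance table to judge whether the Week 16 TEWL values come from skin under the planned treatment would be misled about that child.

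**Working it through.** The SAP states no compliance figure to reproduce, so the check applies its definition to its own schedule.

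**Inputs.** Planned administrations: 4 in regimen 1 (Weeks 0, 4, 8, 12) and 8 in regimen 2 (Weeks 0, 2, 4, 6, 8, 10, 12, 14), from Appendix B, footnote c. Threshold: 80%, from section 4.3.2.4. Exposure duration: last dose date minus first dose date, plus 28 days (regimen 1) or 14 days (regimen 2), same section.

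**Formulas.** For a child who takes the first k doses as planned and none after:
- SAP compliance = k / (doses planned up to dose k) = k/k = 100%, whatever k is.
- Share of the planned course = k/4 or k/8.

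**Results.**

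| Pattern | SAP figure | Share of planned course | Exposure |
|---|---|---|---|
| Regimen 1, Week 12 missed | 3/3 = 100% | 3/4 = 75% | 56 + 28 = 84 days |
| Regimen 1, Week 8 missed, Week 12 given | 3/4 = 75% | 3/4 = 75% | 84 + 28 = 112 days |
| Regimen 2, Week 14 missed | 7/7 = 100% | 7/8 = 87.5% | 84 + 14 = 98 days |
| Regimen 2, Weeks 12 and 14 missed | 6/6 = 100% | 6/8 = 75% | 70 + 14 = 84 days |
| Regimen 2, one mid-course dose missed, then resumed | 7/8 = 87.5% | 7/8 = 87.5% | 98 + 14 = 112 days |
| Full course, either regimen | 100% | 100% | 112 days |

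The first two rows are the clearest contrast. Both children took 3 of 4 doses, but one is reported at 100% and the other at 75%, and only the second falls below 80%. In regimen 2, a missed Week 14 dose alone leaves the child above 80% on either basis; the threshold count changes once two final doses are missed.

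**Effect on the summary.** With about 24 patients (section 1.3), each child wrongly left out of the below-80% group lowers its percentage by 1/24 = 4.2 points.

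**Follow-up doses.** Section 1.4 allows dupilumab as rescue during follow-up, and the SAP does not say whether such a dose can be the last IMP administration. If it can, the cut-off moves past Week 12 and the regimen 1 child in the first row changes from 3/3 = 100% to 3/4 = 75% (the rescue dose not itself being a planned one). The same missed dose would then read differently according to later rescue use.

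**The case against.** The best defence is that this is compliance while on treatment, a recognisable convention with its cut-off stated openly, and that persistence is reported separately. Much of this stands. Exposure duration is tabulated in the same section, and every end-of-course miss above leaves the full-course class of 100 to 113 days: 84 days falls in 72 to 85, and 98 days in 86 to 99. Section 4.3.1.1 gives reasons for permanent discontinuation and a listing. What does not stand is that this makes the percentage clear. The SAP does not label it as on-treatment and gives no companion figure over the planned course, and a skipped final dose need not be a recorded discontinuation.

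Three stronger readings are tempting, and the document does not support them.

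- *Early stopping is hidden.* A child who stops after Day 1 does score 1/1 = 100%, against 1/4 = 25% or 1/8 = 12.5% of the course. But exposure shows 28 or 14 days, and a formal stop is listed.
- *The efficacy result is affected.* Compliance defines neither the ITT nor the mITT population (sections 4.2.2 and 4.2.3) and is not a term in the model of section 4.3.3.1. No estimate, interval or p-value changes.
- *The under-dosing classes, ending "and >20% under planned dosing administrations", are wrong because regimen 1 cannot reach the middle one.* One missed dose really is 1/4 = 25% of the regimen 1 course and 1/8 = 12.5% of the regimen 2 course. The classes follow the share missed; with four doses they are coarse, not incorrect.

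**Conclusion.** The point holds and is minor. By its own definition, the SAP's compliance figure cannot register doses missed at the end of the course. A child who received 75% of the planned course is reported as 100% compliant and left out of the below-80% count, where the same single miss in mid-course in regimen 1 would be counted. This assumes that the earlier doses were taken as planned and that no follow-up dose counts as the last IMP administration.

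The damage is confined to one descriptive percentage and the count built on it. How many children are affected cannot be known from the plan. The planned 15% drop-out is no guide: it was allowed for so that 20 patients remain evaluable, whereas the children of interest here are those who do supply Week 16 data.

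**What to change.** In section 4.3.2.4:

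1. Keep the present figure and label it compliance while on treatment.
2. Add a second percentage, with its own below-80% count, whose denominator is all planned treatment-phase administrations: 4 for regimen 1 and 8 for regimen 2. Do not truncate it at discontinuation; otherwise a child who formally stops after Day 1 would still score 100%.
3. Exclude follow-up rescue doses from both figures, and say so.
4. Present the second figure by dose regimen.
5. List patients who have Week 16 TEWL data but missed their last scheduled dose before Week 16.

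The cost is a few lines of SAP text, minor programming and a slightly less favourable compliance figure. For children who discontinued, the second line measures the share of the course received rather than adherence, which is why both lines should be shown. Dosing, data collection, analysis populations and models are unchanged, and the under-dosing classes can stay as they are.

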4.3.3 Analyses of evaluation variables

4.3.3.1 *Analysis of main evaluation variable(s)*

The primary endpoint will be analyzed on the mITT population. As a sensitivity analysis, it will also be analyzed based on the ITT population.

The calculation of changes (absolute and percent) from baseline will be based on the same number of STS (ie, for absolute change from baseline after 5 STS at W16: Change TEWL at W16 after 5 STS = TEWL value at W16 after 5 STS – TEWL value at baseline after 5 STS).

If a change in spot anatomical location changed versus Day 1 is identified and assessed by the study team as having a significant impact on skin barrier, only visits prior to the location change will be considered in the statistical analysis of TEWL data. Raw data and change (absolute and percent) from baseline will be summarized with descriptive statistics by timepoint.

Profiles over time (from baseline to Week 16) will be generated for individual values (spaghetti plot).

For information purpose as study is not powered (no multiplicity correction will be applied):

- For each number of STS, the evolution of the percent change from baseline over time will be analyzed using a repeated measures analysis of variance with visit, type of skin, interaction between visit and type of skin, age, and baseline value as fixed effects and subject identifier as random effect, at a Type 1 error level of alpha=0.05. In case of heterogeneity at baseline, additional covariates (ie, site, race ...) could be added in this statistical model.
- The following covariance structures will be tested in the REPEATED statement of the PROC MIXED: un, vc and cs at least. The structure with the smallest Bayesian information criteria will be selected for the final model.
- Point estimate and two-sided 95% confidence interval and corresponding two-sided p-value will be reported for each effect. No comparison will be performed.
- If assumption of normal distribution is strongly violated, transformation method could be used: eg, log transformation; normality assumption will be assessed through quantile-quantile plot and Shapiro-Wilk test at 5% Type I error.

4.3.3.2 Analyses of secondary evaluation variables

The secondary endpoints will be analyzed on the mITT populations. Secondary endpoints analysis might be run on the ITT population as sensitivity analysis in case an important number of patients using rescue therapy is observed.

Due to high variability between the 3 adjacent spots for TEWL data in a similar study conducted by the Sponsor, the average of these 3 adjacent spots will not be appropriated. Consequently, TEWL data collected at the same visit from without or before STS measurement on each of the 3 spots within the predefined skin areas will be analyzed by spot separately. The calculation of changes (absolute and percent) from baseline at a visit before/without STS measurement will be based on the same spot (ie, for absolute change from baseline at W2 before STS in spot 1: Change TEWL at W2 before STS in spot 1 = TEWL value at W2 before STS in spot 1 – TEWL value at baseline before STS in spot 1). The calculation of changes (absolute and percent) from baseline at a visit after STS measurement will be based on the same number of STS, as for the primary endpoint.

If a change in spot anatomical location changed versus Day 1 is identified and assessed by the study team as having a significant impact on skin barrier, only visits prior to the location change will be considered in the statistical analysis of TEWL data.

For the analysis of change (percent and absolute) from baseline in TEWL after 5, 10, 15 and 20 STS assessed on each skin group at Week 16, the similar approach, as for the analysis of primary endpoint, will be used. For each number of STS, point estimate, two-sided 95% confidence interval and corresponding two-sided p-value will be reported for each effect. No comparison will be performed.

For the analyses of change (percent and absolute) from baseline in TEWL before/without and after each planned number of STS on each skin group over time:

- Raw data and change (absolute and percent) from baseline will be summarized with descriptive statistics by skin group, number of STS and spot (if applicable), and timepoint. For follow-up period data, change from Week 16 (or last visit prior to use of rescue treatment) will also be reported.
- Profiles over time will be generated for individual values (spaghetti plot) and group means (\pm SEM) for raw data and absolute change from baseline/Week 16 by skin group, number of STS and spot (if applicable).
- As an exploratory analysis, the time to improvement of skin barrier function for lesional and non-lesional skin area measured by TEWL will be summarized for the treatment phase. Improvement is defined as time to the first post-baseline day for which at least 1 TEWL measure of a patient is equal or lower than the TEWL median in the matched healthy volunteers over time. Results might be reported through Kaplan-Meier plot in case of high number of events. Time to improvement of skin barrier function for lesional and non-lesional skin area will also be listed.

For the analyses of change (percent and absolute) from baseline in TEWL AUC (a composite measure before and after 5, 10, 15, and 20 STS) for skin barrier function in each skin group over time:

- As all TEWL values are expected to be positive, area under the TEWL curve will be calculated using the trapezoidal method over the 20 STS (measurement at every 5 STS and all other unplanned number of STS) at each visit. For AUC derivation only, TEWL data performed at unplanned number of STS will be used.
- Raw data and change (absolute and percent) from baseline will be summarized with descriptive statistics by skin group and timepoints. For follow-up period data, change from Week 16 (or last visit prior to use of rescue treatment) will also be reported.
- Box plots over time will be generated for absolute change from baseline/Week 16.
- As exploratory analysis, time to improvement of skin barrier function for lesional and non-lesional skin area measured by TEWL AUC will be summarized for the treatment phase. Improvement is defined as time to the first post-baseline day for which TEWL AUC of a patient is equal or lower than the median, of the corresponding TEWL AUC computed in his/her matched healthy volunteer over time. Results might be reported through Kaplan-Meier plot in case of high number of events.

TEWL conditions (ie, room temperature and humidity, etc.) will be summarized with descriptive statistics by timepoint.

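### The time-to-improvement rules ignore the Day 1 value, so skin already at or below the healthy median at baseline is counted as improved without any change

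*SAP*

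**What the plan says.** SAP section 4.3.3.2 defines two exploratory times to improvement, both for lesional and non-lesional skin during the treatment phase.

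- **TEWL:** the event falls on the earliest day after baseline when "at least 1 TEWL measure of a patient is equal or lower than the TEWL median in the matched healthy volunteers over time". The result is summarised and listed, with a Kaplan-Meier plot if events are numerous.
- **TEWL AUC:** the "first post-baseline day for which TEWL AUC of a patient is equal or lower than the median". The reference is worded differently here: "equal or lower than the median, of the corresponding TEWL AUC computed in his/her matched healthy volunteer over time". The result is summarised, again with an optional Kaplan-Meier plot.

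Three other provisions bear on these rules.

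- Section 4.3.2.2 defines a TEWL baseline for each skin group and STS number, and before STS "a baseline will be defined for each spot, due to strong variability between the 3 adjacent spots".
- Section 4.3.3.2 says that pre-STS TEWL "on each of the 3 spots within the predefined skin areas will be analyzed by spot separately".
- Footnote g of Appendix B (section 8.2) rotates the stripped spot. Spot 1 is used at Weeks 0, 8 and 16 and spot 3 at Weeks 4 and 12, while "At Week 2 STS will be conducted on the second spot within the predefined skin area".

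**The concern.** An outcome called improvement should require a change from where the area started. These rules require only that a later value lies at or below a healthy median. An area that met this condition on Day 1 is neither excluded nor shown apart, so skin that never changed can enter the summaries, the TEWL listing and any Kaplan-Meier plot as improved. The study has no untreated AD group, so no control rate would reveal such events.

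The wording also leaves the derivation open in three places:

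- **Unit of the TEWL event.** At least one measure names neither an STS number nor a spot. Before STS it can be read as the lowest of three spots.
- **Reference.** It is the matched volunteers (plural) for TEWL and the child's own matched volunteer for AUC.
- **Over time.** This may mean pooled over visits or visit by visit.

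Two programmers could follow the text and list different event days for the same child.

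**Working it through.** **1. What follows from the rule alone.** Let B be the Day 1 value, Y(j) the value at post-baseline visit j, and M the healthy median. The event is the first j with Y(j) ≤ M. If B ≤ M and Y(j) = B at every visit, then Y(1) ≤ M and the event falls at the first post-baseline visit with certainty. The modifications list (1.5), the additional analyses (4.3.4), the missing-data section (5.3) and the visit windows (5.5) add no condition on B.

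**2. Simple check with visit noise.** The SAP states no figure for this outcome, so there is none to reproduce. Take an unchanged area whose true level lies d noise SDs above a fixed M. AUC has 5 post-baseline STS visits in the treatment phase (Weeks 2, 4, 8, 12, 16). With independent noise, P(event) = 1 − Φ(d)^5.

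- d = 0: 1 − 0.5^5 = 96.9%
- d = 1: 1 − 0.8413^5 = 58%
- d = 2: 1 − 0.9772^5 = 11%
- d = 3: 1 − 0.99865^5 = 0.7%

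The problem is large near the healthy level and small far above it.

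**3. Simulation with a matched volunteer.** The following inputs are assumed, because the SAP calls the spot variability strong but gives no mean or SD.

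- log TEWL = log(patient/healthy ratio) + child + spot + visit + measurement, all normal, with no drug effect. Volunteers follow the same model with ratio 1.
- Child log-SD is 0.10, 0.25 or 0.40. Spot, visit and measurement log-SD are 0.15, 0.175 or 0.20 each.
- There are 40,000 pairs per scenario. Each range is the minimum to maximum over the 9 combinations.
- Pre-STS visits are Day 1 plus Weeks 1, 2, 3, 4, 6, 8, 12 and 16. The threshold is the own match's median on the same spot over these 9 visits. For any of three spots, it is the own match's median over all spots and visits.
- AUC is one value per STS visit with the Appendix B spot rotation. The threshold is the own match's median over Weeks 0 to 16.

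| Patient/healthy ratio | 1.25 | 1.5 | 2 | 3 |
|---|---|---|---|---|
| One pre-STS spot: called improved by Week 16 | 55-68% | 36-50% | 10-33% | 0.4-15% |
| Share of these already met on Day 1 | 40-65% | 27-59% | 16-51% | 7-41% |
| AUC: called improved by Week 16 | 54-68% | 33-49% | 7-31% | 0.1-14% |
| Share of these already met on Day 1 | 36-64% | 23-58% | 11-50% | 4-41% |
| TEWL read as any of three spots: called improved | 65-91% | 54-76% | 16-44% | 0.5-22% |
| One spot, only areas above the reference on Day 1 | 31-57% | 24-41% | 8-21% | 0.4-10% |
| The same, confirmed at the next visit | 14-24% | 9-14% | 1-8% | 0-3% |

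Repeating the simulation with another seed moved these limits by no more than about 2 percentage points. The least stable are the Day 1 shares at ratio 3, where events are rare.

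**4. The other reading of the reference.** If the TEWL reference is the cohort (taken here as the true healthy median), the Day 1 share for one spot falls to about 30-54% / 16-46% / 5-34% / 0-23% at the four ratios. At 1.25 the total called improved is then 57-74%. The conclusion is the same, with a smaller Day 1 part.

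**The case against.** The strongest reply has five parts.

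- **Weight.** The analysis is exploratory, no test is predefined (5.6), and the SAP does not say that any skin group lies near the healthy level. This stands, and it is why the point is minor and its size conditional.
- **Two causes.** Many of the false events come from a first noisy crossing over several visits and not from Day 1 status. At ratio 2, between 100 − 51 = 49% and 100 − 16 = 84% of one-spot events are of this kind. This also stands. The baseline condition removes only the events already met on Day 1.
- **Context.** The TEWL rule sits in a list whose neighbouring items work by STS number and spot, so that is the natural reading. Agreed. The any-of-three figures show only what the loose wording permits.
- **Visibility.** Individual TEWL profiles are planned and would show low Day 1 values. For AUC, section 4.3.3.2 plans raw-data summaries and, as its display, "Box plots over time will be generated for absolute change from baseline/Week 16". The baseline scatterplots in 4.3.3.3 include AUC. Low Day 1 values could therefore be noticed, but the event counts would still include them.
- **Labelling.** The rule can be read as time to reach the healthy level, where areas already there count at once. That would be acceptable under that name, but the SAP calls it improvement.

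**Conclusion.** The concern holds for both rules. That an unchanged area at or below the reference on Day 1 is counted as improved follows from the text and needs no assumption. How many areas are affected depends on how close patient skin lies to healthy skin, which the SAP does not state. Under the assumptions above, the effect is substantial at 1.25 to 1.5 times the healthy level and small at 3 times when variability between children is low. Severity is minor: one exploratory outcome is affected and the primary endpoint is not.

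**What to change.** In section 4.3.3.2:

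1. Derive the TEWL event separately for each STS number and, before STS, for each spot.
2. State one reference median for TEWL and AUC: same STS number, and same spot before STS; own match or cohort; pooled over visits or visit-specific.
3. Count events only in areas above that reference at baseline, using the TEWL baselines already defined in 4.3.2.2. List areas at or below it separately.
4. Optionally, for pre-STS TEWL only, show events confirmed at the next visit on the same spot beside the first crossing. Do not use this after STS or for AUC, because the stripped spot changes between consecutive STS visits (spots 1, 2, 3, 1, 3, 1 at Weeks 0, 2, 4, 8, 12, 16).

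The cost is SAP wording and programming; no new data are needed. There will be fewer areas at risk and fewer events, and chance crossings near the healthy level remain. After STS and for AUC, Day 1 status comes from spot 1, so a crossing at Week 2, 4 or 12 is on a different spot. The report should say so.
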